APPENDIX I
PERFORMANCE STATUS CRITERIA

ECOG Performance Status Scale		Karnofsky Performance Scale	
Grade	Description	Percent	Description
0	Normal activity. Full active, able to carry on all pre-disease performance without restriction.	100	Normal, no complaints, no evidence of disease.
		90	Able to carry on normal activity; minor signs or symptoms of disease.
1	Symptoms, but ambulatory. Restricted in physically strenuous activity, but ambulatory and able to carry out work of a light or sedentary nature (e.g., light housework, office work).	80	Normal activity with effort; some signs or symptoms of disease.
		70	Cares for self, unable to carry on normal activity or to do active work.
2	In bed < 50% of the time. Ambulatory and capable of all self-care, but unable to carry out any work activities. Up and about more than 50% of waking hours.	60	Requires occasional assistance, but is able to care for most of his/her needs.
		50	Requires considerable assistance and frequent medical care.
3	In bed > 50% of the time. Capable of only limited self-care, confined to bed or chair more than 50% of waking hours.	40	Disabled, requires special care and assistance.
		30	Severely disabled, hospitalization indicated. Death not imminent.
4	100% bedridden. Completely disabled. Cannot carry on any self-care. Totally confined to bed or chair.	20	Very sick, hospitalization indicated. Death not imminent.
		10	Moribund, fatal processes progressing rapidly.
5	Dead.	0	Dead

APPENDIX II
DATA COLLECTION SHEET

Esophageal Brachytherapy / IRB# IP 30

MRN	Date	Tumor Response: CR, PR, SD, PD	Esophageal Ulceration (Yes / No)	Esophageal Fistula (Yes / No)	Esophageal Stricture (Yes / No)	Need for Dilation (Yes / No)
-----	------	--------------------------------	-------------------------------------	----------------------------------	------------------------------------	---------------------------------

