1.4 Rationale

Although patient access to endoscopy centers has expanded and the incidence of esophageal cancer continues to increase, one of the key limiting factors in the more widespread use of esophageal brachytherapy is the limitations of the current single catheter approach. Therefore, in an effort to improve on this technique, patients in our department have been treated using a novel 3-tube technique. This 3-tube technique makes the dose more conformal and reduces the "hot spots" of radiation (doses above the prescription dose) in the esophageal wall. We evaluated the clinical outcomes of the initial thirteen patients treated for medically unresectable, stage 0-IVA, esophageal cancer with our 3-tube design: Five patients were treated with HDR brachytherapy alone and eight were treated with a combination of HDR brachytherapy and external beam radiation therapy. Across all patients, the 18-month local control, disease-free-survival, and overall survival rates were 81%, 74%, and 92%, respectively. Moreover, no patients have suffered a fistula as a result of treatment and only two patients have required dilation for esophageal strictures. A majority of the patients (11 of 13) continue to be free of dysphagia at a median of 17 months of follow-up. These promising initial results have fueled our interest in further innovation of our delivery technique in an effort to broaden the utility of esophageal brachytherapy as well as provide more effect cancer-directed therapy while maintaining a patient's quality of life.

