8.3.3 Adverse Event Evaluation

The investigator or designee is responsible for ensuring that all adverse events (both serious and non-serious) observed by the clinical team or reported by the subject which occur after the subject has signed the informed consent are fully recorded in the subject’s medical records. Source documentation must be available to support all adverse events.

A laboratory test abnormality considered clinically relevant (e.g., causing the subject to withdraw from the study, requiring treatment or causing apparent clinical manifestations, result in a delay or dose modification of study treatment, or judged relevant by the investigator), should be reported as an adverse event.

The investigator or sub-investigator (treating physician if applicable) will provide the following for all adverse events (both serious and non-serious):

- Event term (as per CTCAE)
- Description of the event
- Date of onset and resolution
- **Expectedness of the toxicity**
- **Grade of toxicity**
- **Attribution of relatedness to the investigational therapy/agent- (this must be assigned by an investigator, sub-investigator, or treating physician)**
- Action taken as a result of the event, including but not limited to; no changes, dose interrupted, reduced, discontinued, etc. or action taken with regard to the event, i.e. no action, received conmed or other intervention, etc.
- Outcome of event

Descriptions and **grading scales** found in the NCI Common Terminology Criteria for Adverse Events (CTCAE) version **4.0** will be utilized for agent AE reporting.

An expected adverse event is an event previously known or anticipated to result from participation in the research study or any underlying disease, disorder, or condition of the subject. The event is usually listed in the Investigator Brochure, consent form or research protocol.

An unexpected adverse event is an adverse event not previously known or anticipated to result from the research study or any underlying disease, disorder, or condition of the subject.

Attribution is the relationship between an adverse event or serious adverse event and the study drug. Attribution will be assigned as follows:

- Definite – The AE is clearly related to the study drug.
- Probable – The AE is likely related to the study drug.
- Possible – The AE may be related to the study drug.
- Unlikely – The AE is doubtfully related to the study drug.
- Unrelated – The AE is clearly NOT related to the study drug.

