8.5 Reporting Procedures for Serious Adverse Events

For the purposes of safety reporting, all adverse events will be reported that occur [Please insert appropriate time frame, e.g. on or following first day of RT, on day of registration, etc.] through 30 days after the final dose of study radiation therapy/drug. Adverse events, both serious and non-serious, and deaths that occur during this period will be recorded in the source documents. All SAEs should be monitored until they are resolved or are clearly determined to be due to a subject's stable or chronic condition or intercurrent illness(es). Related AEs will be followed until resolution to baseline or grade 1 or stabilization.

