10.0 CORRELATIVE STUDIES N/A

11.0 STUDY PARAMETERS AND CALENDAR

11.2 Calendar

Patients will be treated weekly for 3 to 6 weeks.

Follow up visits will take place at 3 and 6 month intervals.

A visit window of \pm 1 day is allowed for treatment/procedure visit

A visit window of \pm 7 days is allowed for the 3 and 6 month follow-up visits.

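### Late ulceration, fistula and stricture may be recorded only as an ungraded Yes/No: the form has no grade, onset date or look-back rule, and the adverse-event window closes before the month-3 visit

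*Combined protocol and SAP*

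**What the plan says.** **The form.** Appendix II has one row per entry with a single Date column and these items: "Esophageal Ulceration (Yes / No"), "Esophageal Fistula (Yes / No"), "Esophageal Stricture (Yes / No") and "Need for Dilation (Yes / No"). The data list in Section 3.0 uses the same Yes/No format. Section 12.0 names the same items as measures of effect and adds no definition, grade, method of assessment or look-back period. Nothing says whether the date is that of a visit, a procedure or an onset.

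**The adverse-event record.** Section 8.3.3 asks for a grade and dates of onset and resolution for every adverse event after consent, serious or not. It uses the scales "found in the NCI Common Terminology Criteria for Adverse Events (CTCAE"), version 4.0, and states no end date. Section 8.5 limits the reporting period: it runs "through 30 days after the final dose of study radiation therapy/drug".

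**Follow-up.** Section 6.8 follows patients for 6 months from the initial procedure. Section 11.2 states: "Follow up visits will take place at 3 and 6 month intervals".

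**The comparison.** Sections 3.0 and 14.0 promise to compare patient outcome with historical controls. For the 13 patients treated with the 3-tube technique, Section 1.4 reports no fistula and says that "only two patients have required dilation for esophageal strictures".

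**The concern.** The tissue-damage items are the plan's clinical measures of effect for a new device. Section 1.1 names treatment toxicity as the reason this treatment did not become routine, so they are the results a reader will look for.

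A Yes/No cannot separate a trivial ulcer from a dangerous one. The adverse-event record could supply the missing severity and timing, but its stated period ends before either follow-up visit. For a non-serious lesion that first appears after that, the Yes/No box may be the only planned structured entry.

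A second problem is what Yes means. If one coordinator records what is visible today and another records what has ever happened, the same history gives different answers. With about 5 patients, severity and timing are most of the available information, and they may not be recoverable later.

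**Working it through.** The plan states no figure on this point, so there is nothing to reproduce. The check sets the two records side by side and then works through the calendar.

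**1. What each record holds**

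| | Grade | Onset and resolution dates | Look-back rule | End of period |
|---|---|---|---|---|
| Adverse events, 8.3.3 | CTCAE 4.0 | both | from consent | none stated |
| Adverse events, 8.5 | – | – | start left as a template blank | final dose + 30 days |
| 3.0, 12.0, Appendix II | none | one undefined date per row | none | not stated |

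**2. When the 8.5 window closes**

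Take the first session as day 0, the last dose as day D, and the window end as E = D + 30. The sections give different numbers of sessions, so the whole range is used.

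- 2 weekly sessions (6.1.3): D = 7, E = 37
- 3 sessions (Protocol Summary): D = 14, E = 44
- initial session plus 3 weeks (3.4): D = 21, E = 51
- 6 sessions (Protocol Summary, 6.1.3): D = 35, E = 65
- initial session plus 6 weeks (3.4): D = 42, E = 72

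Take month 3 as day 91 and month 6 as day 182, both counted from the initial procedure.

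- Gap to the month-3 visit: 91 − 72 = 19 to 91 − 37 = 54 days. At the early edge of the 7-day visit window (day 84) the smallest gap is still 84 − 72 = 12 days.
- Gap to the month-6 visit: 182 − 72 = 110 to 182 − 37 = 145 days.
- Share of follow-up inside the window: 37/182 = 20% to 72/182 = 40%.

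On every stated schedule, both follow-up visits fall after the window closes.

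**3. What Yes could mean**

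Consider an ulcer that appears after month 3 and heals before month 6. At month 6 it is a Yes if the item means *ever* or *since last visit*, and a No if it means *present today*. The form permits all three readings.

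**4. Size of an undercount, as an illustration only**

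Under *ever* or *since last visit*, with every lesion noticed and reported, the missed share is zero. Under *present today* it depends on lesion duration L and onset time, neither of which the documents give. Assume six weekly sessions, onset uniform from day 66 (after the window) to day 182 (116 days), and L of 4 to 8 weeks. A lesion is seen at month 3 if its onset falls between day 66 and day 91 (25 days, since each L reaches back to day 63 or earlier). It is seen at month 6 if its onset falls in the last L days.

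- L = 28: (25 + 28)/116 = 53/116 = 46% seen, 54% missed
- L = 42: (25 + 42)/116 = 67/116 = 58% seen, 42% missed
- L = 56: (25 + 56)/116 = 81/116 = 70% seen, 30% missed

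The range is therefore 0% under one reading and 30% to 54% under the other with these assumed durations. One duration is applied to all lesion types, which the documents do not support, so this is not a forecast.

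**5. Scale at n = 5**

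One patient is 1/5 = 20 percentage points. Exact 95% intervals are 0% to 52% for 0/5 and 0.5% to 72% for 1/5. Counts alone say little, which is why grade and timing matter.

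**The case against.** The strongest reply is that much of this is covered elsewhere. Section 8.3.3 has no end date and Section 6.8 follows each event until it resolves or stabilises, so a late lesion could still be graded and dated. Possibly related serious events are reportable even after the study period, so a serious fistula or stricture does not depend on the box. Section 13.1 refers to electronic forms that the documents do not show, and endoscopic follow-up images are planned. The primary objective is dosimetric, and the toxicity objective concerns acute effects. This stands as far as serious events go. For late non-serious lesions it shows that 8.3.3, 6.8 and 8.5 disagree, which leaves the gap open.

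Three stronger readings are tempting and should not be drawn.

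- *The entries are undated.* They are not: Appendix II has a Date column. The fault is that the date is undefined and is not an onset date.
- *A dilated stricture disappears.* It may still appear in the dilation column. That column lacks dates and a reason, though, and Sections 3.0 and 6.1.1 also provide for dilation to insert the applicator, so a Yes there is ambiguous.
- *The comparison is biased towards the new applicator.* The documents do not establish this. Section 1.4 gives a 3-tube fistula count of zero, which undercounting cannot improve on. It gives no ulceration count at all, and its stricture figure counts dilations, which have their own column. Any undercount also requires the *present today* reading, which no section states.

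**Conclusion.** The point holds in a limited form. The items in 12.0 and Appendix II carry no grade, onset date or look-back rule. The 8.5 window closes at about day 37 to 72, before both follow-up visits. Late non-serious lesions may therefore be captured only as an ungraded Yes/No, with mild and severe damage counted alike, and a healed ulcer could be scored No if the form is read as status on the day.

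The calendar result rests only on the stated schedules and on taking month 3 as day 91 and month 6 as day 182. The undercount has no single size: it is zero under one reading and, under the other, depends on durations that have to be assumed. No sample size or error rate is affected, and the primary dosimetric objective is untouched. This is a cheap improvement that should be made before the first patient reaches follow-up.

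**What to change.** 1. In Section 12.0, Appendix II and the matching list in Section 3.0, replace the Yes/No for ulceration, fistula and stricture with the worst CTCAE 4.0 grade since the last visit (0 to 5, with 0 for absent) and the onset date. Define the Date column as the visit date.
2. Replace the dilation Yes/No with the number, dates and reason of dilations since the last visit, separating dilation to insert the applicator from dilation for a stricture after treatment.
3. Report for each patient the worst grade by month 6 and whether the event ever occurred by then. The second is the form comparable with the 3-tube counts in Section 1.4. Those counts are ungraded and come from a series with a median of 17 months of follow-up, so state the difference in duration beside any comparison.
4. Reconcile the 8.5 reporting period with 8.3.3 and with the 6-month follow-up in 6.8, so that it is clear whether late non-serious lesions must be graded.

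This uses the existing visits and a scale the protocol already adopts. The cost is a form revision, an amendment to the text and slightly longer data entry.
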